## 13.6.1. Primary Statistical Analysis

Data will be pooled with historical data and a treatment variable defined (Subgam-VF or Gammaplex IGIV). Log transformed  $sAUC_{(0-\tau)}$ , ( $AUC_{(0-\tau)}$  standardized to one week) will be analyzed using a mixed model fitted including treatment, and allowing for variability to be different between treatment groups. The mean difference (Subgam-VF or Gammaplex IGIV) between treatments with 90% Confidence Interval (CI) will be back transformed to give an estimate of the ratio (Subgam-VF/ Gammaplex IGIV) of  $sAUC_{(0-\tau)}$ . If the resulting 90% CI for the ratio lies within the equivalence limit of (0.80, 1.25), it will be concluded that there is equivalence in  $sAUC_{(0-\tau)}$  and thus the dosing factor of 1.37 for Subgam-VF (in addition to the adjustment for dosing interval) gives equivalent exposure at steady state to Gammaplex IGIV.

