#### **Primary Statistical Analysis**

Data will be pooled with historical data and a treatment variable defined (Subgam-VF or Gammaplex IGIV). Log transformed  $sAUC_{(0-\tau)}$ , ( $AUC_{(0-\tau)}$  standardized to one week) will be analyzed using a mixed model fitted including treatment, and allowing for variability to be different between treatment groups. The mean difference (Subgam-VF or Gammaplex IGIV) between treatments with 90% Confidence Interval (CI) will be back transformed to give an estimate of the ratio (Subgam-VF/ Gammaplex IGIV) of  $sAUC_{(0-\tau)}$ . If the resulting 90% CI for the ratio lies within the equivalence limit of

Page 12 of 87

Name of Sponsor/Company: Bio Products Laboratory Ltd. (BPL) [name]	Name of Manufacturer: Bio Products Laboratory Ltd. (BPL) [name]
Name of Finished Product: Subgam VF Name of Active Ingredient: Immune Globulin (Human)	Protocol identification code: SCIG03 Protocol Synopsis version and date: Version 6, 22 March 2017

(0.80, 1.25), it will be concluded that there is equivalence in sAUC(0-7) and thus the dosing factor of 1.37 for Subgam-VF (in addition to the adjustment for dosing interval) gives equivalent exposure at steady state to Gammaplex IGIV.

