# 8.2. Investigational Treatment

# 8.2.1. Dosing Schedule and Rationale

Subgam-VF is a 16% subcutaneous IgG product. The weekly dose of Subgam-VF administered will be calculated by taking the weekly equivalent of the subject's stable IGIV dose, multiplied by 1.37, a dose adjustment coefficient based on other licensed subcutaneous IgG products. If the subject was already receiving a weekly SCIG IgG there will be no dose adjustment. The Subgam-VF dose should remain the same throughout the study, if a subject's weight changes by >5% compared with baseline (screening) or the previous visit, the dose should be adjusted accordingly with the aim of maintaining a stable dose in terms of mg/kg. If the dosage needs to be increased to achieve the required trough IgG level, then this should first be discussed with the CRO Medical Monitor, who will, if needed, discuss with the Sponsor.

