# 13.2.2.1. Subgam PK population

All subjects in the ITT population who have a pre-dose sample at steady state and at least four post-dose samples at steady state, one of them should be the Steady State Day 7 PK sample. In the case of a subject who provides IgG levels at the PK assessment but does not meet the criteria for inclusion in the Subgam PK population, data will be listed only.

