## 13.2.2.3. PK Dose-Adjustment population

The PK Dose-Adjustment population is the subset of the PK population which excludes subjects in the Subgam PK population who had prior treatment with another subcutaneous weekly IgG product. Thus the PK Dose-Adjustment population includes all the Gammaplex PK population and those in the Subgam PK population who had previous treatment with IGIV. This population is analysed to estimate a refined dose adjustment factor.

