# 13.6. Pharmacokinetic Analyses

The pharmacokinetics of Subgam-VF will be based on absolute and baseline-adjusted (trough adjusted at steady state) values and will be described using a non-compartmental method. Actual sample times rather than nominal times will be used to calculate pharmacokinetic parameters.

The following PK parameters will be calculated for the Subgam PK population: The maximum observed concentration ( $C_{max}$ ), the time at which  $C_{max}$  was apparent ( $t_{max}$ ), the area under the concentration versus time curve within a dosing interval ( $AUC_{0-\tau}$ ) and the systemic clearance (CL).

Pharmacokinetic variables will be summarized descriptively. This analysis will be conducted for subjects 2 to 5 years of age, 6 to 11 years of age, 12 to 15 years of age, all pediatric subjects (2 to 15 years of age), all adult subjects (aged 16 years and over), then for all subjects.

For the Gammaplex PK population,  $sAUC_{0-\tau}$  will be calculated as the area under the concentration versus time curve within a dosing interval (21 or 28 days), standardized to one week i.e.  $AUC_{0-\tau}$  (21 day)/3 or  $AUC_{0-\tau}$  (28 day)/4. For the Subgam PK population,  $sAUC_{0-\tau}$  is equivalent to  $AUC_{0-\tau}$  (i.e. no standardization required as dosing is weekly).

All PK data collected on all subjects in the Subgam PK population will be listed. The PK population i.e. Subgam PK population combined with the Gammaplex PK population (historical data following administration of Gammaplex 5% IGIV) will be used for the primary and secondary statistical PK analyses.

The trough levels of total IgG will be summarized descriptively for all the subjects in the ITT population. Trough levels in the ITT population will be compared with those from the Gammaplex PK population.

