# 13.6.2. Secondary Statistical Analyses

- i. The primary analysis method will be repeated with data derived from baseline-adjusted concentrations.
- ii. A term for dosing interval within treatment will be included in the model described in the primary analysis so that ratios with 90% CI can be presented for Subgam-VF relative to both the 21 day and 28 day dosing interval regimens of Gammaplex.
- iii. The primary analysis model will be extended to include any significant (at the 10% level) covariates or covariate by treatment interactions. Covariates considered for inclusion will include age category, weight, BMI and sex.
- iv. The effect of previous treatment (SCIG or IGIV) on  $AUC_{(0-\tau)}$  in the Subgam PK population will be analysed. If the resulting 90% CI for the ratio lies within the equivalence limit of (0.80, 1.25), it will be concluded that the previous treatment does not affect exposure at steady state. If this is the case then the refined dose adjustment with 90% CI will be presented on the full PK population (in addition to on the PK Dose Adjustment population described below).
- v. In addition, the data from the current study will be restricted to a PK Dose Adjustment population and analysed as per the primary analysis. A refined dose adjustment will be estimated as 1.37/the ratio (Subgam-VF / Gammaplex IGIV) of geometric means for sAUC(0- $\tau$ ) and presented with 90% CI.

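### The primary test credits the 1.37 factor using a pooled group that may include prior-SCIG subjects whose dose was not scaled by 1.37

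*Protocol*

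**What the plan says.** Inclusion criterion 4 (Protocol 6.1) admits subjects on IGIV or weekly SCIG, and no limit is set on either share. IGIV subjects have their weekly-equivalent dose multiplied by 1.37. For the others, section 8.2.1 says "If the subject was already receiving a weekly SCIG IgG there will be no dose adjustment".

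The Subgam PK population (13.2.2.1) is defined by sampling alone: "All subjects in the ITT population who have a pre-dose sample at steady state and at least four post-dose samples at steady state", one of which should be the Day 7 sample. Prior route is not a criterion. Section 13.6 combines this group with the historical Gammaplex group and says that the combined set "will be used for the primary and secondary statistical PK analyses". If the 90% CI for the ratio falls inside the limits, section 13.6.1 concludes that "thus the dosing factor of 1.37 for Subgam-VF (in addition to the adjustment for dosing interval) gives equivalent exposure at steady state". The synopsis likewise says that the factor "gives equivalent exposure at steady state to Gammaplex IGIV".

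Two secondary analyses in 13.6.2 bear on this:

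- **Item iv** compares AUC between prior-SCIG and prior-IGIV subjects. If that CI lies within 0.80 to 1.25, "If this is the case then the refined dose adjustment with 90% CI will be presented on the full PK population", alongside the restricted estimate.
- **Item v**: "the data from the current study will be restricted to a PK Dose Adjustment population and analysed as per the primary analysis". That population (13.2.2.3) "includes all the Gammaplex PK population and those in the Subgam PK population who had previous treatment with IGIV". Its stated output is a refined coefficient, 1.37 divided by the ratio, with a 90% CI.

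The SAP (sections 3 and 14) leaves PK analyses to a separate PK Analysis Plan, which was not available for this review.

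**The concern.** The conclusion is about a conversion factor, but some of the data behind it may come from subjects to whom the factor was not applied in this trial. Their exposure reflects an SCIG dose fixed before the study. The pooled ratio is thus a mixture whose weights depend on who happens to be recruited.

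The Protocol recognises the distinction, since it defines a population without prior-SCIG subjects. Nothing, however, makes the 1.37 conclusion depend on that population. If the pooled CI passed and the item v CI did not, the text would still conclude that 1.37 gives equivalent exposure. The reverse can also occur: prior-SCIG subjects with lower exposure could make the pooled test fail when the factor is adequate.

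The primary objective (5.1), an AUC comparison, is not affected. What is at stake is the 1.37 statement attached to the primary result, and with it the secondary objective of refining the coefficient (5.2).

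**Working it through.** **Inputs from the Protocol.** Limits 0.80 and 1.25, 90% CI (13.6.1). 30 evaluable subjects, log-scale SD 0.181, power above 98% with no difference and 86% with a 10% difference (13.1). Entry dose bands (6.1).

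**Assumptions not in the documents.** Historical group size (30, with 60 as a check); prior-SCIG share *f*; exposure of prior-SCIG subjects relative to those dosed by 1.37, *d*.

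**1. The plan's own power.** The log SD from the CV is √ln(1 + 0.182²) = 0.1805, which agrees with 0.181. With 30 historical subjects, SE = 0.181 × √(1/30 + 1/30) = 0.0467, t(0.95, 58 df) = 1.672 and ln 1.25 = 0.2231. At ratio 1.10, (0.2231 − 0.0953)/0.0467 − 1.672 = 1.06, a power of about 86% (exact: 85.5%). At ratio 1.00 the exact power is 99.8%. The stated figures are therefore reproduced with 30 assumed historical subjects. At ratio 0.90 the same design gives 80%.

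**2. What the pooled test estimates.** If *R* is the true ratio in subjects dosed by 1.37, the pooled Subgam geometric mean ratio is *R* × *d*^*f*. It equals *R* only when *d* = 1 or *f* = 0.

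**3. A range for *d*.** IGIV entry doses of 300 to 800 mg/kg/month, with a 4-week month and multiplied by 1.37, become 300/4 × 1.37 = 103 to 800/4 × 1.37 = 274 mg/kg/week. With a calendar month they become about 95 to 252. The SCIG band is 110 to 300, which is 7% to 9% higher at the limits under the first reading and 16% to 19% under the second. These are entry limits, not mean doses. They show that 9% and 19% are possible under the criteria, not that they are expected.

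**4. Wrong confirmation.** Equivalence was simulated with an unequal-variance 90% CI. The 30 Subgam subjects were a mixture of the two groups, so the spread between groups enters the SE. *R* = 0.80; the ranges run from *d* = 1.09 to *d* = 1.19.

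| Prior-SCIG share | Pooled, 30 historical | Pooled, 60 historical | Prior-IGIV only |
|---|---|---|---|
| 10% | 7%–9% | – | 5% |
| 20% | 10%–17% | 11%–19% | 5% |
| 30% | 13%–27% | 15%–32% | 5% |
| 50% | 22%–54% | 27%–64% | 5% |

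With *d* = 1.00 the pooled figure stays at 5% at every share.

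Hand check at *f* = 0.30, *d* = 1.19, 30 historical subjects:

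- Shift from the limit: 0.30 × ln 1.19 = 0.0522.
- Subgam variance: 0.181² + 0.30 × 0.70 × (ln 1.19)² = 0.0391.
- SE used in the CI: √((0.0391 + 0.0328)/30) = 0.0490.
- Required distance: 1.672 × 0.0490 = 0.0818.
- Chance of passing: 1 − Φ((0.0818 − 0.0522)/0.0467) ≈ 26%, against 27% simulated.

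**5. Missed confirmation.** With *R* = 0.90, *d* = 0.91 and 30 historical subjects, pooled power is 67%, 59% and 43% at shares of 20%, 30% and 50%. Prior-IGIV subjects alone (24, 21, 15) give 76%, 73% and 64%.

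**6. Item iv.** With *R* = 1, the full-population coefficient centres on 1.37/*d*^*f*. At a 20% share that is 1.35 (*d* = 1.09) or 1.32 (*d* = 1.19); at 50% it is 1.31 or 1.26. The 0.80 to 1.25 condition is met in 41% and 14% of trials with 24 prior-IGIV and 6 prior-SCIG subjects, and in 64% and 18% with 15 and 15. The shift is modest and partly screened out.

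**The case against.** The strongest reply is that the sponsor saw the issue and planned for it. Item v repeats the primary model without prior-SCIG subjects, and its ratio and CI will be reported whatever the pooled result. Being analysed in the same way as the primary, it can be read as carrying the same limits. In the wrong-confirmation case at a 30% share, 9% to 22% of trials would show a pooled pass alongside an item v failure, so the conflict would be visible. This shows that the correct estimate will exist. It does not show which result decides, and the text ties the 1.37 conclusion to the pooled one.

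The PK Analysis Plan may already make that link. This cannot be excluded, but the Protocol wording would still need to agree with it.

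The sizes rest on assumed inputs. That stands: at *d* = 1.09 and shares of 10% to 20%, wrong confirmation is only 7% to 10%, and the largest figures need a 50% share, *d* = 1.19 and a true ratio exactly at the limit. The missed-confirmation case also depends on sign. At *R* = 0.90 with *d* = 1.00, pooled power is 80%, higher than in the subset; with *d* = 1.09 it is 88%, 91% and 96% at shares of 20%, 30% and 50%. A loss reappears at a ratio of 1.10 when *d* is above 1.

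Finally, prior-IGIV subjects alone do not isolate 1.37 perfectly. Their comparison still assumes that their weekly-equivalent IGIV doses resemble those of the historical subjects. This also stands and should be stated in the plan.

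**Conclusion.** The concern holds. The pooled analysis suits the primary AUC comparison, but the step from it to a conclusion about 1.37 does not follow when prior-SCIG subjects may be in the group and nothing conditions the conclusion on item v. This follows from the text and needs no numerical assumption.

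The size does need assumptions. With 30 historical subjects and prior-SCIG exposure 9% to 19% higher, wrong confirmation at a true ratio of 0.80 rises from 5% to between 10% and 17% at a 20% share, and to between 13% and 27% at 30%. If the two groups have the same exposure ratio, there is no distortion. The documents give neither the share nor the relative exposure, so confidence in the practical impact is medium. It should be fixed, because the remedy uses a population and model that already exist.

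**What to change.** - **Primary conclusion (13.6.1 and synopsis).** Keep the full PK population for the AUC comparison and word the result as exposure at the study doses relative to Gammaplex.
- **The 1.37 statement.** Base it on item v, in the PK Dose-Adjustment population, with the same 0.80 to 1.25 rule, and say that this result governs.
- **Item iv.** Label the full-population coefficient as supportive. Deleting it is an option but is not needed.
- **Remaining assumption.** State that the restricted comparison assumes similar weekly-equivalent IGIV doses in switching and historical subjects, and summarise both.
- **Power.** Give it for the 1.37 claim by number of evaluable prior-IGIV subjects.
- **PK Analysis Plan.** Make it agree.

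No new data, population or model is required, and no change of dose is suggested. The cost is precision, because fewer subjects carry the 1.37 claim. Power at true ratios of 1.10 / 0.90:

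| Prior-IGIV subjects | 30 historical (assumed) | 60 historical (assumed) |
|---|---|---|
| 30 | 86% / 80% | – |
| 24 | 82% / 76% | 89% / 84% |
| 21 | 79% / 73% | – |
| 15 | 70% / 64% | 77% / 70% |

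With 30 historical subjects, the stated 86% applies to the 1.37 claim only if about 30 prior-IGIV subjects are evaluable.

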# 13.6.2. Secondary Statistical Analyses

- i. The primary analysis method will be repeated with data derived from baseline-adjusted concentrations.
- ii. A term for dosing interval within treatment will be included in the model described in the primary analysis so that ratios with 90% CI can be presented for Subgam-VF relative to both the 21 day and 28 day dosing interval regimens of Gammaplex.
- iii. The primary analysis model will be extended to include any significant (at the 10% level) covariates or covariate by treatment interactions. Covariates considered for inclusion will include age category, weight, BMI and sex.
- iv. The effect of previous treatment (SCIG or IGIV) on  $AUC_{(0-\tau)}$  in the Subgam PK population will be analysed. If the resulting 90% CI for the ratio lies within the equivalence limit of (0.80, 1.25), it will be concluded that the previous treatment does not affect exposure at steady state. If this is the case then the refined dose adjustment with 90% CI will be presented on the full PK population (in addition to on the PK Dose Adjustment population described below).
- v. In addition, the data from the current study will be restricted to a PK Dose Adjustment population and analysed as per the primary analysis. A refined dose adjustment will be estimated as 1.37/the ratio (Subgam-VF / Gammaplex IGIV) of geometric means for sAUC(0- $\tau$ ) and presented with 90% CI.

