#### **Pharmacokinetics:**

The pharmacokinetics (PK) of Subgam-VF will be described by using a non-compartmental method. The trough levels of total IgG will be summarized descriptively for all the Intent-to-Treat (ITT) subjects and compared with historical data for Gammaplex 5%. Pharmacokinetic variables will be summarized descriptively. The primary PK parameter will be sAUC(0-τ).

All PK parameters will be calculated based on absolute (uncorrected) and baseline-adjusted (i.e. trough-adjusted at steady state) concentrations.

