# 4.3. Benefit / Risk Statement

Published data has shown that subcutaneous IgG (SCIG) use in subjects with PID provides protection which is comparable to that found with IGIV therapy.

Infusions of IgGs given subcutaneously (SCIG) were initially used in patients who were unable to tolerate IgG administered either through intravenous (IV) or intramuscular (IM) routes. SCIG has the advantage in that it can be self-administered at a time and location more suitable to the individual and without the need for assistance from a trained professional (other than during the initial training period). This convenience has been associated with an improvement in quality of life.

This form of infusion requires no venous access. Unlike IGIV which is infused directly into the intravascular compartment, SCIG must diffuse first into the lymphatic system and is then Page 17 of 87

subsequently carried into the blood stream via the thoracic duct, therefore with SCIG the intravascular concentration of IgG increases more gradually, peaking at 48-72 hours. The rate IgG enters the circulation appears to be the main driver of systemic tolerability and as such the incidence of systemic adverse events appears to be much lower with SCIG therapy than with IV infusion. Also division of the dose into weekly fractions produces more consistent IgG levels without the peaks and troughs experienced with monthly IGIV infusions. However, with SCIG therapy because some of the IgG is already equilibrating into the extracellular fluid before all of the IgG has entered the bloodstream; and also due to binding and/or degradation of the IgG in subcutaneous tissue, the maximum serum concentration of IgG can be on average 61% of the level achieved with IGIV.

As with any blood product, viral safety is a concern. Subgam-VF undergoes a stringent multistep process, including solvent/detergent treatment, nanofiltration, and a terminal low pH incubation of the finished product, to reduce the risk of potential viral contaminants and enhance the safety of the product.

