## 11. ASSESSMENT OF PHARMACOKINETICS

# 11.1. Pharmacokinetics of Subgam-VF for Total IgG Levels

All subjects will undergo a PK assessment (see Appendix IV, Table 2 and 3 for the sampling time points).

Where possible, samples from Steady State Day 1 (24 hours after the infusion at Week 21 or if delayed, up to Week 25) onwards may be collected at the subject's home by an appropriately qualified member of the study team. Alternatively a Home Health Agency may be utilized to take the PK samples outside of the investigational site. The subject would be required to sign an IRB/EC approved consent form to permit the site to share the subject's details with the agency in order for them to collect the sample.

The following PK variables for total IgG levels will be determined for the PK population:

- AUC $_{(0-\tau)}$  area under the plasma concentration-time curve of the dosing interval.
- $sAUC_{(0-\tau)}$  area under the plasma concentration-time curve of the dosing interval standardized to one week. This will be calculated for the historical data only.

- Cmax maximum concentration in plasma.
- $t_{max}$  time to reach the maximum concentration in plasma.
- CL– systemic clearance.

The timing of the collection of blood samples for PK should be as per Table 2. The scheduling has been selected to ensure achievement of steady state of Subgam-VF.

A variation of <10% is allowed in the timing for samples as follows:

Steady State Day 1 (24 hours)  $\pm$  2 hours,

Steady State Day 2 (48 hours)  $\pm$  4 hours

Steady State Day 3 (72 hours)  $\pm$  6 hours

Steady State Day 5 (120 hours)  $\pm$  8 hours

Steady State Day 7 (168 hours)  $\pm$  12 hours.

All PK parameters will be calculated based on absolute (uncorrected) and baseline-adjusted (i.e. trough-adjusted at steady state) concentrations.

Details of the PK methods will be outlined in a PK Analysis Plan. The PK Analysis Plan will be finalized before database lock.

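### Secondary analysis i compares trough-subtracted AUC between weekly SC and 3- or 4-weekly IV dosing, so its ratio falls far below 1 even when total exposure is identical

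*Protocol*

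**What the plan says.** The primary analysis (Protocol Section 13.6.1) takes log sAUC, fits a model with treatment as the factor, and back-transforms the difference to a Subgam-VF/Gammaplex ratio with a 90% CI. Its decision rule begins: "If the resulting 90% CI for the ratio lies within the equivalence limit of (0.80, 1.25), it will be concluded" that the two are equivalent.

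For Gammaplex, sAUC is the "area under the concentration versus time curve within a dosing interval (21 or 28 days), standardized to one week", that is, AUC divided by 3 or 4. For Subgam-VF there is "no standardization required as dosing is weekly" (both Section 13.6).

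Section 13.6.2, item i, and the same item in the synopsis add: "The primary analysis method will be repeated with data derived from baseline-adjusted concentrations". The synopsis defines the adjustment: "All PK parameters will be calculated based on absolute (uncorrected) and baseline-adjusted (i.e. trough-adjusted at steady state) concentrations". Protocol Sections 11.1 and 13.6 and SAP Section 5.4 define it the same way. Item i gives no separate estimand, limits or interpretation.

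On the shape of the two profiles, Section 4.3 says that with subcutaneous dosing "the intravascular concentration of IgG increases more gradually, peaking at 48-72 hours", and that "division of the dose into weekly fractions produces more consistent IgG levels without the peaks and troughs experienced with monthly IGIV infusions".

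**The concern.** In these subjects the steady-state trough holds any endogenous IgG plus product carried over from many earlier infusions. Subtracting it removes most of the exposure the study is meant to compare. What remains is mean concentration minus trough. That quantity shrinks when the interval is shorter and when input is slower, and weekly subcutaneous dosing differs from 3- or 4-weekly intravenous dosing in both respects. Section 4.3 itself predicts the flatter profile.

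Item i therefore puts a difference in schedule and route into a ratio that will be read as relative exposure. A successful primary analysis would be reported beside a prespecified ratio far below 0.80. Explaining that away after the fact would look like discarding an unfavourable result.

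There are two related problems. The subcutaneous rise above trough is small, so measurement error can make some adjusted AUCs zero or negative. These cannot be logged, and neither document says how to handle them. Also, the instruction to calculate all PK parameters on adjusted concentrations covers clearance, which has no useful meaning on that scale.

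**Working it through.** **Inputs from the documents.** Dosing intervals of 7 days (Subgam-VF) and 21 or 28 days (Gammaplex); division by 3 or 4; limits 0.80-1.25; subcutaneous peak at 48-72 hours; PK samples on days 0, 1, 2, 3, 5 and 7; log-scale SD 0.181 and 30 evaluable subjects.

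**Assumptions.** IgG half-life 20-40 days; first-order subcutaneous absorption *ka* of 0.3-1.0/day, which puts the modelled peak at 1.9-2.9 days; one- or two-compartment kinetics; the size of measurement error. None of these is in the documents.

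**The plan's own figure.** The plan gives no figure for item i. Its power statement for the primary analysis does reproduce. The number of historical subjects is not stated; taking it as 30, SE = 0.181 × √(1/30 + 1/30) = 0.0467. Two one-sided 5% tests then give 99.8% power at a ratio of 1.00 and 86.2% at 1.10, against the stated figures of more than 98% and 86%. That calculation concerns unadjusted sAUC.

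**Share of AUC left after trough subtraction.** Let *k* = ln 2 / half-life and *τ* = dosing interval. The share left is 1 − Ctrough/Cavg.

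- Intravenous: Ctrough/Cavg = *kτ*·e^(−*kτ*) / (1 − e^(−*kτ*)).
- Subcutaneous: Ctrough/Cavg = *kτ*·[*ka*/(*ka* − *k*)]·[e^(−*kτ*)/(1 − e^(−*kτ*)) − e^(−*ka·τ*)/(1 − e^(−*ka·τ*))].

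The adjusted ratio is the true sAUC ratio × (subcutaneous share / intravenous share).

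**Worked case: half-life 30 days, *ka* 0.7/day (peak 2.2 days), true ratio 1.00.** *k* = 0.0231/day.

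- IV, 21 days: *kτ* = 0.485; Ctrough/Cavg = 0.485 × 0.616 / 0.384 = 0.777; share left 22.3%.
- IV, 28 days: *kτ* = 0.647; Ctrough/Cavg = 0.647 × 0.524 / 0.476 = 0.711; share left 28.9%.
- SC, 7 days: Ctrough/Cavg = 0.1617 × 1.034 × (5.697 − 0.0075) = 0.9515; share left 4.85% (4.68% by trapezoid at the planned sampling times).
- Adjusted ratio: 0.0485/0.223 = 0.22 against 21-day dosing and 0.0485/0.289 = 0.17 against 28-day dosing.

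**Full range at a true ratio of 1.00.**

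| | Against 21-day IV | Against 28-day IV |
|---|---|---|
| Share left, SC | 2-8% | 2-8% |
| Share left, IV | 17-32% | 22-41% |
| Adjusted ratio, one compartment | 0.12-0.27 | 0.09-0.21 |
| Adjusted ratio if SC input were instantaneous | 0.35-0.36 | 0.27-0.29 |

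The last row isolates the interval: before any effect of route, the ratio is already close to 7/21 or 7/28. Adding two-compartment models and *ka* down to 0.2/day gives 0.06-0.39 over both intervals, or 0.06-0.28 when the peak is held to 48-72 hours. A constant endogenous level cancels and leaves the ratio unchanged.

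**What it would take to reach 0.80.** For true ratios from 0.80 to 1.25 the one-compartment adjusted ratio runs from 0.80 × 0.088 = 0.07 to 1.25 × 0.265 = 0.33. Reaching 0.80 needs true exposure of 0.80/0.265 = 3.0 to 0.80/0.088 = 9.0 times that of Gammaplex.

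**Same product against itself.** Gammaplex 21-day over 28-day at equal weekly exposure is 0.223/0.289 = 0.77 in the worked case, 0.77-0.78 across half-lives in one compartment, and 0.78-0.83 in two compartments. It should be 1.00.

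**Non-positive adjusted AUCs.** Simulated Subgam-VF profiles at the six planned times (linear trapezoid, half-life 25-35 days, *ka* 0.5-1.0/day, independent proportional error) give this percentage of subjects at or below zero:

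| Trough taken as | 2% error | 3% error | 5% error |
|---|---|---|---|
| Pre-dose sample | 0-5% | 1-14% | 9-26% |
| Mean of pre-dose and Day 7 | 0-1% | 0-6% | 2-17% |
| Lower of the two | 0-0.2% | 0-1.7% | 0.6-6% |

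**Clearance.** If CL is dose/AUC, adjustment multiplies it by 1/share: 12-51 times for subcutaneous and 2.5-5.9 times for intravenous dosing (one compartment).

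**The case against.** The arithmetic and the direction are not in dispute. The case against rests on what the documents leave open.

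- **Unseen plan.** The protocol does not say which trough is used or give a formula, and it sends PK detail to a PK Analysis Plan that is not among the documents. It is true that a rule for non-positive values could sit there, and that the simulated rates depend heavily on the trough chosen. The main point is unaffected: at steady state the pre-dose and Day 7 troughs have the same expected value, so the choice does not move the expected ratio. The protocol itself already names both the adjustment and the comparison.
- **Limits not restated.** Item iv in the same list repeats 0.80-1.25 and states a conclusion; item i does neither. It may intend only a ratio with its interval. This is fair, and applying the limits to item i is a reading of the reference to the primary method. The ratio would still mislead without a formal verdict.
- **Small consequence.** The primary analysis and the dose refinement in item v use unadjusted sAUC, and nothing is gated on item i. This stands in full and sets the weight of the point.
- **Clearance.** No formula is given, and Section 13.6 lists CL for the Subgam PK population only, so the intravenous inflation may describe something never calculated. The subcutaneous inflation remains if CL is dose/AUC.
- **Assumed kinetics.** Half-life, absorption and model form are all assumed. They set the size of the shortfall; no setting tried brought the ratio above 0.39 at equal exposure.

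**Conclusion.** The concern holds. As written, item i estimates a ratio of within-interval fluctuation and presents it through the method used for relative exposure. At identical total exposure the expected value is about 0.1-0.3 under one-compartment kinetics and at most 0.39 on the widest grid examined. The direction follows from the shorter interval and slower input, which the protocol itself describes; the exact size rests on the assumed half-life, absorption and model form. The frequency of non-positive AUCs and the inflation of clearance are conditional on the trough definition, the measurement error and the CL formula. The point should be corrected, but it does not threaten the primary conclusion or the refined dose coefficient.

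**What to change.** Reword item i in Protocol Section 13.6.2 and in the synopsis, for example: *Trough-adjusted values will be summarized descriptively by product and dosing interval as a measure of within-interval fluctuation. No Subgam-VF/Gammaplex exposure ratio or equivalence conclusion will be drawn from them.* In the synopsis Pharmacokinetics paragraph, Protocol Sections 11.1 and 13.6 and SAP Section 5.4, exclude CL from the parameters calculated on trough-adjusted concentrations. Carry both changes into the PK Analysis Plan and define there which sample is the trough.

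The cost is matching edits in six places, with whatever amendment approval they require, and no new data or sampling. One supportive comparison is lost, but it says little about whether exposure is equivalent. A lighter alternative keeps the ratio but states that the limits do not apply and that it reflects fluctuation. That would still need a rule for values that cannot be logged, since simply dropping them would bias the geometric mean upward.
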